change in HR and SC responses to the interview relative to baseline. 2) A subjective unit of distress (SUD) scale which is commonly used will be rated by the child using a developmentally appropriate SUD rating (i.e., “scary feeling score,” 0-3 or 4). Prior research with young children as well as our experience suggests that children age 4 and older understand the rating scale and can provide these data. Similar to our pilot work, children will provide six ratings during exposure or trauma-related activities and parents will record these ratings. In TF-CBT, the child ratings will be recorded by the therapist. The first rating will occur before the exposure/activity, four during the activity with the highest being recorded as the peak rating and one after the exposure/activity. Changes in trauma-related negative appraisals: The *Post-Traumatic Cognitions Inventory-child version (CPTCI)*, is a 25-item child report of negative trauma-related cognitions. The CPTCI has demonstrated excellent psychometrics and no age-related differences in scores for children ages 6-18. The measure will be administered with children ages 6 to 12 (~78% of the sample). Expectancy of negative outcomes (ENOs): The ENOs measure, modified from [name] et al. and similar to Deacon et al., is a 3-item parent report of the child’s perceived expectancy of a negative outcome that is rated (0 to 100) before and after the trauma-related activity. Children’s fear toleration (CFT): Similar to Deacon et al., parents will rate (0-100) the extent of the child’s fear toleration when participating in the trauma-focused activity. Therapeutic worry and alliance will also be examined as potential mechanisms of change which will be measured using the treatment worry questionnaire at baseline only (child and parent version) and the Therapeutic Alliance Scale for Children (TASC, parent, child, and therapist version) administered the same assessment time periods as the HR and SC (i.e., Weeks, 0, 2,4 = Step One & 0,5,8= TF-CBT and at post-assessment) (Keeley et al. 2011). As indicated in Table 1, the mechanism of change measures will occur at post-assessment too. The “trauma-related activity” will be a 5 minute semi-structured interview that consists of the same guide that is used during the HR and SK test. After these measures are completed the parent and child will be asked independently 6 questions about their experiences talking about what happened, including how they may have changed. These responses will be used to triangulate the quantitative measures.

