
**c.6.6. Plan to explicitly address whether the intervention engages the mechanism.** To demonstrate that the hypothesized mediators changed before the primary outcomes, we will administer the assessments of the mediators and primary outcomes during the course of treatment. Parents will complete the primary outcome measures TSCYC-PTS total and the Child Sheen Disability Scale- parent version during the five outcome assessment periods, and at the beginning of each therapy session and/or parent-child meeting. We used the parent rating of child PTS since the TSCYC is for children ages 4 to 12 and to minimize the burden of children completing another measure every session.

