**Primary Aim 3:** We will examine four potential mechanisms of change on both Step One and TF-CBT including fear arousal, maladaptive cognitions, expectancy of negative outcomes, and fear toleration. The analysis of mechanism of change will have two phases. First, we will run univariate latent difference score (Goldstein, #1) models on the longitudinal observations of potential mediator and outcome variables. Since the fear-arousal variables (HR and SC) that both assess sympathetic nervous system activation are typically correlated, and combining physiological responses into single indices is common (e.g.,), we will attempt to combine them into a single index. LDS incorporates features of latent growth curve modeling and cross-lagged regression models and is appropriate in research on mechanisms of change. We will compare univariate LDS models for time invariant and time-varying proportional coefficients as well as a no change score LDS model to find the model that best depicts the mechanism. The model selection process will run independently across all potential mediators and outcome variables. Second, we will run bivariate LDS by pairing between two univariate LDS models that have been identified. These pairings include mediator-mediator, mediator-outcome, and outcome-outcome types. We will identify coupling pattern by comparing three candidate models (within the bivariate LDS models): no coupling between the two series, unidirectional coupling in which the change in one variable leads to the other, and bidirectional coupling or cross lagged pattern. For the secondary hypothesis 3.2., we will add a time varying qualitative indicator for direct exposure activities and its interaction with the change component. A significant interaction term indicates the mechanisms are different for the more direct (i.e., Step One) and less direct exposure activities (i.e., TF-CBT). We will also use open coding methods to capture a range of categories related to children and parents experience of talking about the trauma narrative (a trauma related activity used during the mechanism of change measures) and changes that may have occurred during treatment. Thematic content analysis (Patton, 2002; Corbin & Strauss, 2008) will be used to establish the range of participants' experiences and changes.

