## Amendment to the analysis plan 2.11.2022

**Aim 1.** We applied linear mixed-effect models (LME; SAS Institute Inc, 2015) with repeated measures to detect whether the two treatments performed differently at post-, 6- and 12-month assessments. Instead of 5% alpha we used a more stringent 2.5% alpha (Piaggio et al, 2012) for the non-inferiority analysis with the .41 margin. For the non-inferiority margin for the PCL-5, the clinically significant change threshold is 10 points although adult PTSD trials have used -5 (Foa et al., 2019) to -10 (Mathersul et al., 2019) points. We used -8.8 as the margin which was based on an expert panel and prior studies with adults (Acierno et al., 2017). Due to attrition (27.87%) being higher than planned (15%) and enrollment (N = 183) lower than the planned enrollment (N = 216), the power analysis was based on the actual randomization of 183 participants (SC-TF-CBT=91; standard TF-CBT=92).

**Aim 2.** We used backward stepwise logistic regression with predictors with  $p < .01$ . Besides predictors in the unadjusted model, demographics including children gender, age and race were included in the partially adjusted

model. In addition, three child primary outcomes were added for the full adjusted model.

**Aim 3.** Instead of LDS we used Linear mixed-effect models (LME) with repeated measures were used to detect whether the potential mechanisms of change declined significantly over time and whether the rate of change differed by treatment group with standard TF-CBT coded as 0 and Step One responders coded as 1. Further, we tested mediation and moderated mediation. If moderated mediation was not found mediation was tested with two regression equations: the first equation included mediators regressed on treatment condition and outcome variables at baseline; the second equation included outcomes regressed on treatment condition, mediators, and outcome variables at baseline. If there was no evidence of significant mediation, linear regression model (OLS) was applied to test the linear estimates as predictors for both outcome (TSCYC-PTS and CSDS-P).

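### The amended Aim 3 models name no visits and adjust only for baseline outcome, so a significant mediator-outcome path cannot be read as the mediator driving symptoms

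*Combined protocol and SAP*

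**What the plan says.** Section c.6.6 gives the purpose of measuring mediators and primary outcomes repeatedly during treatment: "To demonstrate that the hypothesized mediators changed before the primary outcomes". Parents complete TSCYC-PTS and CSDS-P at the start of each session or parent-child meeting. Under the within-session ratings in the same section, fear toleration and negative expectancy are rated after the trauma-related activity. Section c.6.5 adds a further sample: "As indicated in Table 1, the mechanism of change measures will occur at post-assessment too".

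Section c.8.3 (Primary Aim 3) planned bivariate LDS models that compare no coupling, "unidirectional coupling in which the change in one variable leads to the other, and bidirectional coupling or cross lagged pattern". Section c.9 powers Aim 3 on the unidirectional form.

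The amendment of 2.11.2022 changes this: "Instead of LDS we used Linear mixed-effect models (LME) with repeated measures were used to detect" decline over time and group differences in rate of change. Where moderated mediation is not found, mediation rests on two regressions. In the first, "the first equation included mediators regressed on treatment condition and outcome variables at baseline"; in the second, "the second equation included outcomes regressed on treatment condition, mediators, and outcome variables at baseline". If there is no significant mediation, "linear regression model (OLS) was applied to test the linear estimates as predictors for both outcome". The group variable codes standard TF-CBT as 0 and Step One responders as 1.

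**The concern.** Hypothesis 3.1 is a claim about mechanism, and c.6.6 recognises that such a claim needs the mediator to change first. The coupling models were the part of the plan that compared the two directions. The replacement trend models ask whether a mechanism measure falls and whether it falls at different rates by group. They do not ask which series moves first. The two regressions contain only the baseline outcome, and the OLS step names no covariates.

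Suppose a child's fear rating or negative cognitions simply mirror how symptomatic the child is that week. The mediator then correlates with the later outcome beyond baseline, because both carry the symptom change since baseline. The outcome equation and the OLS step would report this as a mediator effect. The in-treatment outcome scores that could tell the two explanations apart appear in none of the mediation or OLS models as described.

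**Working it through.** **1. The plan's own figure.** Section c.9 states more than 80% power for an effect of 0.29 with 184 children, and a detectable 0.33 for the CPTCI. Treating the effect as a correlation, power = Φ(atanh(r)·√(n−3) − 1.96).
- r = 0.29, n = 92 (one condition): 80.4%. With n = 184: 98.0%.
- CPTCI: 0.78 × 92 = 72 children, detectable r = 0.326.

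The stated figures reproduce as per-condition values. They belong to the directional LDS model and do not carry over to the amended regressions.

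**2. What each model contains.**
- LDS (c.8.3): both series over time, with direction compared.
- Mediator equation (amendment): treatment and baseline outcome. No visit, no baseline mediator.
- Outcome equation (amendment): treatment, mediator and baseline outcome. No visit, no in-treatment outcome.
- OLS step (amendment): the linear estimates, read here as mediator slopes. No time window.

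**3. Simulation with no mediator effect.** The mediator only reads out the current outcome.
- Outcome: Y(k+1) = .9·Y(k) − .3 + N(0, .5), four occasions, the fourth being post.
- Mediator: M(k) = loading × Y(k) + N(0, .8).
- Groups: 66 and 40 children. The 66 is 92 × (1 − .2787) from the amendment. The 40 is an assumption: the pilot response rate in c.1.3 would give 91 × .7213 × .776 ≈ 51.
- Model: post outcome on group, mediator slope and baseline outcome, two-sided .05. The OLS step is taken to carry the same baseline adjustment, which the amendment does not state.

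False significance of the mediator-outcome path:

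| Mediator slope and adjustment | Loading .6 | Loading .3 |
|---|---|---|
| Post sample included, baseline outcome | about 99% | about 60% |
| In-treatment only, baseline outcome | about 75% | about 29% |
| In-treatment only, also outcome at last mediator visit | about 5% | about 5% |

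**4. The two-equation test in the same model.** Calling it mediation only when both the treatment-to-mediator and mediator-to-outcome paths are significant, loading .6, post sample included:
- no group difference: about 5%;
- a .41 SD group drift over the three intervals: about 15%.

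**5. A second model with different assumptions.** Carry-over .7, loading .5, three occasions, 66 against 66 children or 51 Step One responders.
- Mediator and outcome both at post: path falsely significant in 99.8–100% (80–87% at loading .3).
- Mediator at mid-treatment, baseline outcome only: 58–72%.
- Also adjusted for mid-treatment outcome and baseline mediator: about 5%, with false mediation about 1% or less.
- False mediation with both at post: about 5% with no group difference, 12.5% at 0.26 SD, 24% at 0.43 SD, 52% at 0.68 SD.
- Group of responders only: selection alone shifts the post outcome by about 0.27 SD and gives 7%. Selection added to a 0.43 SD difference gives 38%.

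**The case against.** A reader might infer that reverse causation would be declared mediation in 99% of trials. It would not. That figure concerns one path of two. The trial expects comparable outcomes, and the amendment's Aim 4 text refers to non-inferiority results. With no group difference the joint test stays near 5%, so this part of the objection stands.

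It does not clear the OLS step, which is what the amendment turns to when mediation is absent and which tests only the mediator-outcome association. The amendment speaks of predictors there and does not call the step mediation. The error would lie in reading such a predictor as a mechanism under Hypothesis 3.1.

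A reader might also infer that the analysis disregarded sampling order or used same-visit values. The documents do not say so. They are silent on visits and on the form of the moderated-mediation model. HR, SC and CPTCI have samples at Weeks 0, 2 and 4 or 0, 5 and 8, with post at week 13, so an ordered analysis was possible. Order alone suffices in some worlds: when the mediator trails symptoms by a full visit, the second model gives about 5% with a mid-treatment mediator. It does not suffice when the mediator mirrors current symptoms (58–75% across the two models at loadings of .5 and .6).

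**Conclusion.** The point holds for direction. As written, the amended Aim 3 models cannot support the statement that mediators changed first, and a significant mediator-outcome path or OLS predictor should not be read that way. Depending on the assumed loading and visits, false significance of that path runs from about 29% to nearly 100% where the mediator mirrors current symptoms. It falls to about 5% once the outcome at the mediator visit is adjusted for. These sizes rest on assumed loadings, carry-over and group sizes; the inflation and its removal appear under both sets of assumptions.

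False mediation by the two-equation test is a smaller risk: about 5% without a group difference, rising as one appears. Comparing Step One responders with all standard TF-CBT children can itself create such a difference, because responder status depends on symptoms after baseline.

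Aim 3 is explanatory, although c.8.3 labels it a primary aim. Nothing here affects the Aim 1 non-inferiority conclusion.

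**What to change.** In the Aim 3 amendment:
- State the visits that supply the mediator and the outcome.
- Build each mediator from in-treatment samples only (Weeks 0, 2, 4 or 0, 5, 8 for HR, SC and CPTCI; the session series for SUD, ENOs and CFT), with the outcome measured later.
- In the outcome equation and the OLS step, adjust for baseline outcome, baseline mediator, and the TSCYC-PTS or CSDS-P score at the visit of the last mediator sample. That score is taken at session start, before fear toleration and expectancy are rated, so the adjustment respects the order within the session.
- Report any model that uses post-assessment mediator values, and the OLS step if left unadjusted, as association and not mediation.
- Note beside the results that the responder-only group is selected on symptoms after baseline.

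The cost is revised wording and a re-run on data the protocol already planned to collect. Mediator estimates become somewhat less precise without the post sample. As a rough guide, 183 × (1 − .2787) = 132 completers give 80% power for a lagged correlation of about 0.24.

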**Within session ratings.** Parents will rate fear toleration and negative expectancy after each trauma-related activity in therapy sessions and parent-child meetings. As in previous NIH-funded clinical trials (PI: [name], study therapist [name], R34MH070827-01A1; 1RC1MH-088969-01), therapist-directed sessions will be video taped. We will systematically identify the child’s participation in the trauma-focused activity within each session and have parents review that segment via video (~15 min.) during the beginning of the time when the parent meets with the therapist. These research procedures will not significantly influence treatment outcome as discussing with the parent what the child completed in therapist-led sessions is current protocol for both treatments, and similar procedures have been used in previous trauma-focused clinical trials with children 3-12. This procedure allows the parent to have direct observation of the child and allows the parent time to process the observations with the therapist. Viewing video segments will not be needed when there are conjoint sessions. For the at-home parent-child meetings, the parent will complete the ratings immediately after the meetings. Children will complete the *CPTCI* at the beginning of Weeks, 0, 2,4 in Step One & 0,5,8 in TF-CBT and the SUDS rating during treatment. For Step One, measures will be in the parent’s *Stepping Together* book, and therapists will collect these measures at each meeting and will remind parents about the measures during the phone meetings. Since Step One and TF-CBT occur within different timeframes (6wks vs. 3mo), the physiological measures will be administered based on when components are covered and during scheduled in-office visits for Step One patients: at session 1, after the coping skills components, and after four exposures in Step One or the trauma narrative in TF-CBT (Table 1). The frequency of four potential mechanism of change measures (e.g., fear based arousal measure (subjective unit of distress), trauma-related negative appraisals, expectancy of negative outcomes, and fear toleration) will be 12 for both conditions. Step One patients will not complete these measures during parent-child meetings 1 and 2 as these meeting occur directly after the first therapist meeting.

**c.6.7. Fidelity Measures.** All of the fidelity measures were successfully utilized in the pilot trials of SC-TF-CBT.

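### For expectancy (ENOs) and fear toleration (CFT), parents rate the mechanism and both amended Aim 3 outcomes, and no quantitative analysis is planned that could separate a mechanism from shared parent perception

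*Combined protocol and SAP*

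**What the plan says.** **Mechanisms.** Section c.6.5 says the ENOs measure "is a 3-item parent report of the" child's perceived expectancy of a negative outcome. It also has parents rate the child's fear toleration from 0 to 100. Section c.6.6 repeats this for treatment sessions: "Parents will rate fear toleration and negative expectancy after each trauma-related activity in therapy sessions and parent-child meetings". The other two mechanisms are fear arousal (heart rate, skin conductance and child distress ratings) and cognitions (CPTCI). They come from a device or the child.

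**Outcomes.** Section c.6.6 states: "Parents will complete the primary outcome measures TSCYC-PTS total and the Child Sheen Disability Scale- parent version". Its reason for a parent-rated symptom outcome is practical: "We used the parent rating of child PTS since the TSCYC is for children ages 4 to 12", together with child burden. Rater independence is not discussed.

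**Amended analysis (Amendment to the analysis plan 2.11.2022, Aim 3).** The groups are "standard TF-CBT coded as 0 and Step One responders coded as 1". If moderated mediation is not found, two equations follow: "the first equation included mediators regressed on treatment condition and outcome variables at baseline", and "the second equation included outcomes regressed on treatment condition, mediators, and outcome variables at baseline". If mediation is not significant, a "linear regression model (OLS) was applied to test the linear estimates as predictors for both outcome (TSCYC-PTS and CSDS-P". No covariates are given for this last step, and the term *linear estimates* is not defined.

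**Safeguards.** Section c.7 says participants cannot be blinded. Section c.6.5 adds six open questions, put independently to parent and child, to triangulate the quantitative measures. No quantitative Aim 3 analysis with another informant is described.

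**The concern.** Hypothesis 3.1 is about the child: a change in the child's expectancy or fear toleration should lead to a change in the child's symptoms and impairment. For ENOs and CFT, the regressions relate one set of parent ratings to another. If the parent's view of the child changes during treatment, through relief, the parent's own distress or investment in the therapy, both ratings can move together while the child's mechanism does nothing.

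Four mechanisms and two outcomes make eight pairs, and four of those pairs are parent on parent. They hold both inhibitory-learning measures. The fallback regression deserves most attention. It runs when mediation is not found, it needs no group difference in the mediator, and hypothesis 1.1 expects comparable improvement in the two arms. At stake is whether a positive ENOs or CFT result can be described as a mechanism.

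**Working it through.** **The plan's own figure.** Section c.9 gives more than 80% power for an effect of 0.29 with 184 children, under the original latent difference score (LDS) model. It cannot be rebuilt, because no variances or stabilities are given. As a rough proxy, Fisher-z power for a correlation of .29 (two-sided 5%) is 98.0% at n = 184 and 80.4% at n = 92. The documents give no error rate or power for the amended regressions, so there is nothing else to reproduce.

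**Sample size (approximate).** The amendment reports 91 and 92 randomised and 27.87% attrition. Section c.1.3 gives a pilot Step One response rate of 77.6%.
- Standard TF-CBT: 92 × 0.7213 = 66.4
- Step One responders: 91 × 0.7213 × 0.776 = 50.9
- Total: about 117

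**Null model.** Let v be the share of variance in each rating due to parent perception P, and let ρ be the correlation of P between baseline and post. The child's true symptoms T (stability .5 assumed) and true mechanism m are independent.
- Outcome: Y = √(1−v)·T + √v·P
- Mediator: M = √(1−v)·m + √v·P, over the 12 ratings that section c.6.6 plans

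There is no mechanism effect, yet M and Y at post correlate v.

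**Unadjusted OLS on mediator level (closed form).** Rejection = Φ(atanh(v)·√(N−3) − 1.96) + Φ(−atanh(v)·√(N−3) − 1.96). With N = 117 and v = .10, atanh(.10)·√114 = 1.07, so rejection is Φ(−0.89) + Φ(−3.03) = 18.8%.

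**Simulation.** 2,500 runs per cell, N = 117, two-sided 5% assumed. *Adjusted* means baseline outcome and treatment are in the model.

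| Mediator term | ρ | v = .10 | v = .20 | v = .30 |
|---|---|---|---|---|
| Slope, adjusted | .5 | 15.7% | 48.6% | 83.1% |
| | .8 | 7.2% | 13.8% | 32.6% |
| | 1.0 | 5.1% | 4.8% | 4.7% |
| Slope, unadjusted | .5 | 8.8% | 20.2% | 36.6% |
| | .8 | 5.3% | 7.9% | 12.0% |
| | 1.0 | 5.1% | 4.9% | 4.2% |
| Level, adjusted | .5 | 14.9% | 45.6% | 81.4% |
| | .8 | 10.8% | 31.5% | 59.6% |
| | 1.0 | 8.2% | 19.6% | 34.1% |
| Level, unadjusted (closed form) | any | 18.8% | 58.1% | 91.1% |

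At v = 0 the four tests reject 4.8% to 5.3%, as they should. A separate run (8,000 per cell, simple change score, baseline outcome only) gave 15.7%, 47.1% and 81.5% at ρ = .5, and about 7%, 14% and 29% at ρ = .8. Taken together, the adjusted change results are about 15/47/82% at ρ = .5, 7/14/30% at .8 and 5% at 1.0.

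**Why ρ matters.** A slope carries √v·(P at post − P at baseline), which vanishes when perception is fully stable. A level keeps P whatever ρ is.

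**Indirect effect (both paths significant).** If treatment does not move the mediator, false indirect effects stay at or below about 5%, even at v = .40. If it does (0.8 SD assumed), then at v = .20 the rate is 17% to 41% for level. For slope it runs from 5% (ρ = 1) to 43% (ρ = .5).

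**The case against.** Several points on the other side are sound.

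- **Size.** The documents give neither v nor ρ. A reader might infer that the regressions will reject because of shared perception, or that a 10% share triples the error rate. Neither follows. The tripling needs ρ near .5 with a baseline-adjusted change score, or a level score with little or no adjustment. With slopes and stable perception there is no inflation.
- **Mediation.** Shared perception alone does not produce a false indirect effect. The mediator rating must also differ by group.
- **Origin.** The original LDS plan used the same parent-rated outcomes, so the amendment did not create the overlap.
- **Theories.** A reader might infer a contest tilted towards inhibitory learning. Section b.2 includes both theories for a broader, more integrated account, and no test declares a winner. The informant split is not fully clean either: in Step One, parents write down the child's distress ratings.
- **Measurement.** ENOs and CFT are tied to specific activities that the parent has led, attended or watched on video, so they are not global impressions. Parent-rated outcomes cover ages 4 to 12 and are collected every session.
- **Same rater.** That one caregiver completes every form is a reasonable inference, not a stated rule.

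These points limit what can be said about size. They do not supply a quantitative check. Full stability of perception is also doubtful on the plan's own account. Hypothesis 1.1 expects parenting stress, depression and PTSD symptoms to improve, and the Potential Risks section cites research in which parent distress about the trauma fell during TF-CBT.

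**Conclusion.** The concern holds in a limited form. For ENOs and CFT, the mechanism and both Aim 3 outcomes come from unblinded parents, and no planned quantitative analysis could show whether an association reflects the child or the rater. The predictor test and the mediator-to-outcome path can exceed 5% with no true mechanism. Over v = .10 to .30 and ρ = .5 to 1.0, the tabulated rates run from nominal to about 91%. The result depends heavily on whether *linear estimates* are slopes or levels and on the covariates used, and the amendment states neither.

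The figures rest on assumed v and ρ, n of about 117, symptom stability of .5 and a two-sided 5% test. They show what is possible, not the error rate of this trial. The documents do not support reading a positive ENOs or CFT result as false. They support only that, with parent ratings on both sides, such a result does not by itself establish a mechanism.

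**What to change.** In the Aim 3 part of the amendment:

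1. Keep the TSCYC-PTS and CSDS-P models.
2. Define *linear estimates*, and put the baseline outcome and treatment condition in the OLS fallback, to match the second mediation equation. This makes the test explicit but does not cure rater overlap: in the table, adjustment lowers the rate for levels and raises it for slopes when ρ is below 1.
3. Repeat the ENOs and CFT models on outcomes the parent does not rate: the UCLA PTSD Index, the child-version K-SADS symptom count and CSDS-C for ages 7 to 12, and the evaluator-rated CGI-S for all ages. Table 1 schedules these at baseline, mid, post and follow-up. Sections c.6.8 and c.7 still name the ADIS, and c.6.8 the CPSS, so state which instruments were used.
4. Report both sets side by side with confidence intervals. Describe an association seen only in the parent-parent models as possibly due to a shared rater. Do not make significance in the smaller subset a pass/fail rule.

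The cost is wording and extra regressions on data in hand. The amendment is written in the past tense, so label these as added sensitivity analyses.

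The limits are real. Ages 4 to 6 have no child-rated outcome, CGI-S is coarser and partly informed by the caregiver, and none of these outcomes is collected every session. Power also falls. If ages are evenly spread (7/9 = 78% matches the plan's figure for ages 6 to 12), ages 7 to 12 are 6/9 of 117, or 78 children. The correlation detectable with 80% power, tanh(2.80/√(n−3)), then rises from about .26 to about .31.
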